6.1.5 Overdosage

Overdose is not anticipated in the context of a clinical trial. Study product will be administered to subjects. There is no known antidote for baricitinib. However, if a site inadvertently gives a subject excess baricitinib, the site should contact the Sponsor. The subject should receive supportive therapy based on the subject's signs and symptoms.

Reports of acute toxicity and/or death following overdosage of glucocorticoids are rare. In the event of overdosage, no specific antidote is available; treatment is supportive and symptomatic.

6.2 Preparation/Handling/Storage/Accountability

6.2.1 Acquisition and Accountability

Investigational products (IP) will be shipped to the site either directly from participating companies, from the Sponsor, or from other regional or local drug repositories. All other supplies should be provided by the site. Multiple lots of each IP may be supplied.

Study products received at the sites will be open label, unless specified in the protocol-specific Manual of Procedures (MOP) or pharmacy manual. See the MOP Appendices for detailed information on the preparation, labeling, storage, and administration of investigational products.

Accountability

The site PI is responsible for study product distribution and disposition and has ultimate responsibility for study product accountability. The site PI may delegate to the participating site's research pharmacist responsibility for study product accountability. The participating site's research pharmacist will be responsible for maintaining complete records and documentation of study product receipt, accountability, dispensation, storage conditions, and final disposition of the study product(s). Time of study drug administration to the subject will be recorded on the appropriate data collection form (CRF). All study product(s), whether administered or not, must be documented on the appropriate study product accountability record or dispensing log. The Sponsor's monitoring staff will verify the participating site's study product accountability records

Appendix D - ACTT-4: Baricitinib/Remdesivir vs Dexamethasone/Remdesivir and dispensing logs per the site monitoring plan. Refer to the protocol-specific MOP for details on storing study medications.

Destruction

After the study treatment period has ended or as appropriate over the course of the study after study product accountability has been performed, used active and placebo product can be destroyed on-site following applicable site procedures with a second staff member observing and verifying the destruction.

Unused product at the end of the study should be saved until instructed by the Sponsor.

6.2.2 Formulation, Appearance, Packaging, and Labeling

Remdesivir component

Remdesivir may be supplied in two formulations:

- The lyophilized formulation of remdesivir is a preservative-free, white to off-white or yellow, lyophilized solid containing 100 mg of remdesivir to be reconstituted with 19 mL of sterile water for injection respectively and diluted into IV infusion fluids prior to IV infusion.
- The concentrated liquid solution is supplied as a single-dose glass vial containing 100 mg/20 mL (5 mg/mL) of remdesivir that is a sterile, preservative-free, clear, colorless to yellow, aqueous-based concentrated solution to be diluted into 0.9% sodium chloride infusion bag prior to administration by intravenous infusion.

Remdesivir will be labeled according to manufacturer specifications. For complete details of the preparation, packaging and administration, please see the package insert and the MOP.

Baricitinib component

Baricitinib tablets are film-coated, immediate-release tablets. The 2 mg tablet is light pink and oblong. Each tablet contains 2 mg of baricitinib and the following inactive ingredients: croscarmellose sodium, magnesium stearate, mannitol, microcrystalline cellulose, ferric oxide, lecithin (soya), polyethylene glycol, polyvinyl alcohol, talc and titanium dioxide.

Oral placebo component

Placebo tablets match the active product in appearance. The placebo tablets contain lactose monohydrate, microcrystalline cellulose, croscarmellose sodium, and magnesium stearate. The coating for the placebo tablet is identical to that of the corresponding active tablet listed above.

Study interventions (baricitinib and placebo) will be supplied by the sponsor or its designee in accordance with current Good Manufacturing Practice (cGMP).

Dexamethasone component

According to the package insert, dexamethasone is available as **4 mg per mL** in a 5 mL multi-dose vial. It is a sterile solution of dexamethasone sodium phosphate in water for injection for intravenous (IV).

Intravenous placebo for dexamethasone component

Appendix D - ACTT-4: Baricitinib/Remdesivir vs Dexamethasone/Remdesivir

Intravenous normal saline placebo matches the active dexamethasone product in volume and appearance. It is supplied in single-use vial.

A label with the statement “Caution: New drug -Limited by Federal Law to investigational use” will be placed on the immediate package.

6.2.3 Product Storage and Stability

The Pharmacy Manual provides instructions for the preparation, handling, and storage of baricitinib drug product and placebo, dexamethasone drug product and placebo and remdesivir, and describes site responsibility and accountability for the administered products.

See most recent version of package insert and information as posted on the Emmes website.

6.2.4 Preparation

Refer to the protocol-specific MOP for details about preparation of all study products.

6.3 Measures to Minimize Bias: Randomization and Blinding

6.3.1 Randomization

Randomization will be stratified by:

- Site
- Severity of illness at enrollment (by ordinal scale)
 - Hospitalized, on non-invasive ventilation or high flow oxygen devices, OR
 - Hospitalized, requiring supplemental oxygen

The randomization procedure will be described in the MOP.

6.3.2 Blinding and Masking Procedures

As both arms are receiving remdesivir, the remdesivir product is not blinded and study infusions can be labeled accordingly.

The baricitinib/placebo component is blinded. Baricitinib and placebo tablets are identical in appearance.

The dexamethasone/placebo IV component is blinded. Dexamethasone and intravenous placebo are identical in appearance.

6.3.2.1 Unblinding at end of study

Unblinding of the study will occur after all subjects enrolled have reached the end of study, these visits are monitored, and data is cleaned or if the DSMB recommends unblinding. Data through Day 29 will be locked prior to the completion and lock of Day 60 data. DMID and the SDCC will be unblinded after the Day 29 database lock. Clinical sites will not be unblinded to subject-level treatment assignments until after the Day 60 database lock.

6.3.2.2 Unblinding for worsening clinical status

If a subject's clinical status worsens to require mechanical ventilation (ordinal 7), the treating clinician may request unblinding in order to use the prior treatment assignment to inform future treatment. See [section 6.5.4](#) for preferred alternatives prior to unblinding. Any unblinding for this purpose will be tracked by the Sponsor, and sites that frequently unblind subjects in this ordinal scale category may have enrollment curtailed by the Sponsor.

6.3.2.3 Unblinding for adverse event

If a Serious Adverse Event occurs, that is thought to be related to the study drug, and the treating clinician believes that knowledge of the treatment arm may change the therapy provided to the patient, the individual subject can be unblinded. If unblinded for SAE, the investigator may decide to have the blinded study product and/or remdesivir infusions discontinued based on the adverse event that led to unblinding and the benefit-risk analysis. The subject should remain on study through the Day 60 visit. The procedure for emergency unblinding will be further detailed in the Manual of Operations.

6.4 Study Intervention Compliance

Each dose of study product will be administered by a member of the clinical research team who is qualified and licensed to administer the study product. Administration and date, and time, will be entered into the case report form (CRF).

6.5 Concomitant Therapy

6.5.1 Permitted Concomitant Therapy and Procedures

For patients that are eligible for the study, other therapy received prior to enrollment with any other experimental treatment or off-label use of marketed medications that are intended as specific treatment for COVID-19 or the SARS-CoV-2 infection (i.e., post-exposure prophylaxis [PEP]) must be discontinued on enrollment. There is no waiting period between discontinuation of these treatments and administration of study products. However, these prior treatments and their end date should be documented on the Concomitant Medication form in the Advantage eClinical system.

There are two scenarios in which outpatient experimental treatment or off-label use of marketed medications that are intended as specific treatment for COVID-19 do not need to be discontinued. First, subjects who are taking another antiviral for a concurrent infection (e.g. lopinavir/ritonavir for HIV, etc.) or another existing medical condition (e.g. hydroxychloroquine for lupus, etc.) may continue with the treatment. Note that these treatments may be thought of as an off-label medication for COVID-19, however, because they were being used prior to study enrollment for another indication, they are allowable.

Second, if there is a written policy or guideline for the local standard of care and treatment of COVID-19 patients or SARS-CoV-2 infection (i.e., not just an individual clinician decision), continuation of these outpatient medications is permitted (except for dexamethasone and

Appendix D - ACTT-4: Baricitinib/Remdesivir vs Dexamethasone/Remdesivir

baricitinib as noted below). There should be plans on how the concomitant drugs are stopped in case of additive toxicities.

On August 23, 2020, the FDA issued an EUA for COVID-19 convalescent plasma for the treatment of hospitalized patients with COVID-19. The NIH COVID-19 Treatment Guidelines were updated on September 1, 2020 and concludes that “there are insufficient data to recommend either for or against the use of convalescent plasma for the treatment of COVID-19”. According to the NIH Guidelines and the EUA Fact Sheet for Health Care Providers, convalescent plasma should not be considered the standard of care for the treatment of patients with COVID-19. However, if a site has adopted convalescent plasma as part of their institutional standard of care for the treatment of COVID-19 patients, it is allowed as described above.

VTE prophylaxis is recommended for all patients unless there is a major contraindication such as active bleeding events or history of heparin-induced thrombosis.

6.5.2 Prohibited Concomitant Therapy

As the study is comparing baricitinib to dexamethasone, additional baricitinib, dexamethasone and other glucocorticoids are prohibited unless the subject worsens and requires invasive mechanical ventilation (see Section 6.5.4). In addition, if oral study product is held for more than two days and the clinical condition requires, an open-label (off-study) dexamethasone or other anti-inflammatory agent may be added while the oral study product is held (Section 6.1.4). Exceptions to the steroid prohibition include: mineralocorticoids for standard indications are permitted (e.g., adrenal insufficiency, shock) and low-dose prednisone as part of immunosuppression regimen for solid organ-transplant patients is allowed (e.g., prednisone 5 mg po daily).

Strong inhibitors of organic anion transporter 3 (OAT3) such as probenecid are prohibited during the study.

Concomitant use of any other experimental treatment or off-label use of marketed medications intended as specific treatment for COVID-19 or SARS-CoV-2 infection, and not specified in the local or NIH COVID-19 Treatment Guidelines are prohibited. Specifically, use of any biologic therapy not specified on the written policy or guideline are prohibited including: monoclonal antibodies targeting cytokines (e.g., TNF inhibitors; interleukin-1[IL-1], IL-6 [tocilizumab or sarilumab]), or T-cells (e.g., abatacept); monoclonal antibodies targeting B-cells (e.g., rituximab, and including any targeting multiple cell lines including B-cells); JAK inhibitor(s) (e.g., baricitinib, imatinib, gefitinib, acalabrutinib, tofasitinib); and any type of interferon, convalescent plasma, or immunoglobulin (IgG) therapies for COVID-19. Similarly, the concomitant use of hydroxychloroquine to treat COVID-19 is prohibited unless it is included in the local institutional treatment guidelines (and even then, it is discouraged given the interaction with remdesivir).

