Appendix D - ACTT-4: Baricitinib/Remdesivir vs Dexamethasone/Remdesivir

7. Lymphopenia (absolute lymphocyte count <200 cells/ μ L, $0.20 \times 10^3/\mu$ L).
8. Received five or more doses of remdesivir including the loading dose, outside of the study as treatment for COVID-19.
9. Pregnancy or breast feeding (lactating women who agree to discard breast milk from Day 1 until two weeks after the last study product is given are not excluded).
10. Allergy to any study medication.
11. Received convalescent plasma or intravenous immunoglobulin [IVIg] for COVID-19, the current illness for which they are being enrolled.
12. Received any of the following in the two weeks prior to screening as treatment of COVID-19:
 - More than one dose of baricitinib for the treatment of COVID-19;
 - Other small molecule tyrosine kinase inhibitors (e.g. imatinib, gefitinib, acalabrutinib, etc.);
 - monoclonal antibodies targeting cytokines (e.g., TNF inhibitors, anti-interleukin-1 [IL-1], anti-IL-6 [tocilizumab or sarilumab], etc.);
 - monoclonal antibodies targeting T-cells or B-cells as treatment for COVID-19.

Note: receipt of anti-SARS-CoV-2 mAb prior to enrollment (e.g. bamlanivimab) for their current COVID-19 illness is not exclusionary
13. Use of probenecid that cannot be discontinued at study enrollment.
14. Received 6 mg or more of dexamethasone po or IV (or equivalent for other glucocorticoid) in one day, or more than one day, in the 7 days prior to time of randomization. *Note: 6 mg dexamethasone dose equivalents include 40 mg prednisone, 32 mg methylprednisolone and 160 mg hydrocortisone.*
15. Received ≥ 20 mg/day of prednisone po or IV (or equivalent for other glucocorticoids) for ≥ 14 consecutive days in the 4 weeks prior to screening.
16. Have diagnosis of current active or latent tuberculosis (TB), if known, treated for less than 4 weeks with appropriate therapy (by history only, no screening required).
17. Serious infection (besides COVID-19), immunosuppressive state, or immunosuppressive medications that in the opinion of the investigator could constitute a risk when taking baricitinib or dexamethasone.
18. Have received any live vaccine (that is, live attenuated) within 4 weeks before screening, or intend to receive a live vaccine (or live attenuated) during the study. *Note: Use of non-live (inactivated) vaccinations including SARS-CoV-2 vaccine is allowed for all subjects.*

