In ACTT-4, non-study product (off-study) baricitinib, dexamethasone and other glucocorticoids are prohibited unless the subject worsens to require invasive mechanical ventilation (ordinal score 7). Mineralocorticoids for standard indications are permitted (e.g., adrenal insufficiency, shock). Low-dose prednisone as part of immunosuppression regimen for solid organ-transplant patients is allowed as part of standard of care (e.g., prednisone 5 mg po daily).

If additional (off-study) baricitinib, dexamethasone or another glucocorticoid is given when a subject is not an ordinal scale category 7, the investigator should file a protocol deviation for use of the prohibited medication and decide whether the blinded study products should be discontinued. The subject should remain on study and continue with the SOA as described in the protocol though the Day 60 visit. An exception to this is when oral study product is held for more than 2 days and the clinical condition requires that an open-label (off-study) dexamethasone or other anti-inflammatory agent be added while the oral study product is held (see Section 6.1.4).

- The preference is to continue study medication as originally assigned (i.e. continue blinded baricitinib or placebo and continue blinded dexamethasone or placebo) as well as the remdesivir infusions. The subject should remain on study though the Day 60 visit.
- Recognizing the treating clinician may request to stop the randomized blinded study medication, the next preferred option is that the baricitinib/placebo po component and the dexamethasone/placebo IV component are discontinued without unblinding. This will allow the treating clinician to pick any regimen needed for the subject. In this scenario, remdesivir infusions should continue and the subject should remain on study though the Day 60 visit.
- If the treating clinician needs to know prior treatment, the site investigator can request that the subject treatment assignment be unblinded. This is the least preferred option as it unblinds treatment assignment. However, it is available to ensure clinicians have information available to give their patients optimal care. In this scenario, remdesivir infusions should continue and the subject should remain on study through the Day 60 visit.

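### Appendix D (ACTT-4) contradicts itself on glucocorticoids taken at baseline or for non-COVID indications: eligibility admits users that the steroid ban does not provide for

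*Protocol*

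**What the plan says.** All references are to Protocol Appendix D (ACTT-4).

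- **Eligibility (5.2).** Item 15 excludes on this condition: "Received ≥ 20 mg/day of prednisone po or IV (or equivalent for other glucocorticoids) for ≥ 14 consecutive days in the 4 weeks" before screening. Item 14 applies only to days at 6 mg or more of dexamethasone or equivalent, and its note adds that "6 mg dexamethasone dose equivalents include 40 mg prednisone, 32 mg methylprednisolone and 160 mg hydrocortisone". Item 17 lets the investigator exclude for immunosuppressive medication judged a risk, but does not require it.
- **Permitted therapy (6.5.1).** Drugs for a concurrent infection or another existing condition may continue, since "because they were being used prior to study enrollment for another indication, they are allowable". The examples are an HIV antiviral and hydroxychloroquine for lupus. No steroid is mentioned.
- **Prohibited therapy (6.5.2).** The rule is that "additional baricitinib, dexamethasone and other glucocorticoids are prohibited unless the subject worsens and requires invasive mechanical ventilation". Exceptions follow. One is temporary: an open-label anti-inflammatory while oral product is held for more than 2 days (also in 6.1.4). The others are "mineralocorticoids for standard indications are permitted (e.g., adrenal insufficiency, shock) and low-dose prednisone as part of immunosuppression regimen for solid organ-transplant patients".
- **Progression section (6.5.4).** The ban is repeated: "dexamethasone and other glucocorticoids are prohibited unless the subject worsens to require invasive mechanical ventilation (ordinal score 7"). The same exceptions are restated. For any other off-study use before that point, "the investigator should file a protocol deviation for use of the prohibited medication and decide whether the blinded study products should be discontinued". Follow-up on study continues.

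**The concern.** A patient on a modest long-term steroid dose for a disease unrelated to COVID-19 can be randomized without breaching any fixed criterion. From then on the protocol points both ways: one section suggests the drug may continue, and two others prohibit it and call its use a deviation. Sites will resolve this differently.

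Three things are at stake.

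- **Patient care.** Following the ban as written would withhold an eligible patient's existing treatment.
- **Data.** The same act would be a deviation at one site and ordinary care at another. It could also prompt a decision to stop blinded product, and discontinuation or suspension of study product for any reason is a listed safety endpoint.
- **The comparison.** A glucocorticoid is part of the randomized contrast, so a rule that removes background glucocorticoid does not act alike on the two arms.

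The same uncertainty covers a new non-COVID need. The exception that mentions adrenal insufficiency and shock may not reach the drug class a site would think of.

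**Working it through.** There is no sample size or power figure to reproduce. The check is a cross-reading of sections, plus the protocol's own dose equivalence.

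**1. Who is admitted.** Item 14's note sets 6 mg dexamethasone equal to 40 mg prednisone. Item 15's 20 mg prednisone is therefore 6 × 20/40 = 3 mg dexamethasone. Take a patient on 10 mg prednisone daily for a rheumatic disease:

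| Rule | Threshold (prednisone equivalent) | Excludes 10 mg/day? |
|---|---|---|
| Item 14 | 40 mg or more in a day | No |
| Item 15 | 20 mg/day or more for 14 or more consecutive days | No |
| Item 17 | Investigator's opinion | Only at discretion |

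The synopsis and 5.2 word item 14 differently on the number of days, but the daily dose threshold is the same, so the result does not change.

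**2. What happens to that patient's steroid.**

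- Under 6.5.1 it is a drug used before enrollment for another indication, and on that reading it continues.
- Under 6.5.2 and 6.5.4 it is an off-study glucocorticoid before category 7. The patient has no transplant, the drug is not a mineralocorticoid and oral product is not being held, so no named exception applies. Giving it is a deviation.

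**3. Whether 6.5.1 settles it.** The 6.5.1 carve-out for dexamethasone and baricitinib belongs to its second scenario (locally written treatment policy), not to the other-indication scenario. If 6.5.1 already covered baseline steroids, the transplant exception in 6.5.2 would be unnecessary. If it does not, non-transplant users have no stated allowance. Neither reading makes all the passages consistent.

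**4. Adrenal insufficiency and shock.** The clause names mineralocorticoids. Section 2.2.4.1 treats the classes as distinct, saying that dexamethasone lacks mineralocorticoid activity, and item 14 lists hydrocortisone among glucocorticoid equivalents. Whether hydrocortisone for either indication is exempt or a deviation cannot be read from the text.

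**5. Arm contents if the ban is followed.**

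| | Study glucocorticoid during the IV course | Prednisone equivalent |
|---|---|---|
| Arm 1 (baricitinib) | None; the IV product is saline | 0 mg/day |
| Arm 2 (dexamethasone) | 6 mg dexamethasone daily | 40 mg/day |

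Arm 2's 40 mg/day exceeds any chronic dose that item 15 lets through (below 20 mg/day). The difference lasts at most 10 in-hospital doses (6.1.2), after which neither arm receives a study glucocorticoid.

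**The case against.** The strongest reply is that nothing in the protocol orders a stable baseline drug to be stopped. The ban is worded around additional, off-study agents. Its stated reason is to protect the comparison of baricitinib with dexamethasone. Section 6.5.2 introduces its list of exceptions with a word that need not make it exhaustive, and 6.5.1 supplies a permissive reading. The penalty is also limited: a deviation is filed, stopping blinded product is optional, and follow-up continues. On the shock clause, a ban on glucocorticoids needs no exception for pure mineralocorticoids, so the drafters probably meant to allow steroid treatment for those indications.

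Much of this stands, and it limits the point. A reader might infer that the protocol forbids indicated steroids outright and leaves only the baricitinib arm uncovered. The document does not support that. The ban is also lifted at invasive ventilation and while oral product is held, 6.5.1 points the other way, and the arm difference arises only if sites actually withhold the baseline drug. No passage predicts arm-specific harm. Nor does ACTT-2's post-randomization corticosteroid use (2.2.3.1) measure the problem, because indications are not given.

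The reply does not remove the conflict. That 6.5.1 can be read permissively is one half of the contradiction. Section 6.5.4 restates the exceptions without the open-ended wording and attaches the deviation rule. The held-product exception does not help a patient whose oral product continues. If the intent of the shock clause must be guessed against its wording, the wording needs correcting.

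**Conclusion.** The point holds as an internal contradiction with a safety consequence, and it should be corrected. Eligibility admits chronic glucocorticoid users below 20 mg/day prednisone equivalent. Section 6.5.1 can be read as allowing them to continue, while 6.5.2 and 6.5.4 prohibit the drug before ventilation without an exception that fits them. The adrenal insufficiency and shock exception is ambiguous as to drug class.

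The unequal effect on the arms is an inference from what each arm contains. It assumes that a site follows the ban and withholds the baseline steroid, and it is confined to the IV course of at most 10 in-hospital doses. The document does not give the number of baseline users, or how many sites would read the text either way, so no effect on the primary comparison can be calculated. No view is taken on which clinical rule is right.

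**What to change.** Reconcile exclusions 14, 15 and 17 with sections 6.5.1, 6.5.2 and 6.5.4, so that every patient admitted on a baseline glucocorticoid is either explicitly covered by the exceptions or explicitly excluded. State which drug class is meant where adrenal insufficiency and shock are named, in both 6.5.2 and 6.5.4. The sponsor's clinicians choose the rule; what matters here is that all the passages give the same one, and that use the rule permits is not logged as a prohibited-medication deviation.

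The cost is a few lines of text, with the synopsis criteria aligned. If exclusion is chosen, some otherwise eligible patients are lost; the document does not say how many. No new eCRF field is needed: 6.5.3 already records systemic corticosteroids from Day -7 through Day 29, including after discharge, and 9.4.7 already plans subgroups by prior dexamethasone and other prior steroid use.
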